## **Examination Schedule**

Clinical examinations will be performed by IATS certified physicians and visits will be scheduled by the IATS certified clinical coordinator. Study visits will be scheduled for sometime in the year after children have reached 10 years of age and ideally around 6 months after the birthday. Non-study visits may be performed at the discretion of the investigator.

10.0 Years
Examination Information, Interim History, Reading
Manifest Refraction, Cycloplegic E-ETDRS Vision
Clinical Examination: Motility/Stereo, Biomicroscopy, Biometry/keratometry, Tonometry, Pachymetry , Cycloplegic Refraction,
Imaging Optic Disc Photos, Nerve Fiber Layer OCT, Anterior Chamber OCT

## **CHAPTER 3. Clinical Examination**

### **Primary Outcome Examination at Age 10 Years**

A clinical examination will be performed at age 10 years by the site investigator including biomicroscopy, retinoscopy, tonometry, and indirect ophthalmoscopy. Optical biometry, keratometry, and pachymetry will also be performed.

Visual acuity assessment using the E-ETDRS protocol will be performed by certified site personnel; patients should be in their best optical correction as determined by the PI either recently or just before the EVA test.

### **Discontinuation of CL Use Prior to Examination**

If a child randomized to CL correction discontinues CL use prior to the age 10 year assessment and has not received a secondary IOL, then the child will wear the aphakic correction in a trial frame for the visual assessment or a CL with a close spherical power can be on hand and a trial frame can be used for residual correction.

### **Discontinuation of Spectacles Prior to Examination**

If spectacles are still indicated for a child in the IOL group and the child discontinues their use prior to the age 10 year examination, the spectacles prescribed will be worn during the visual assessment. If the refraction has changed based on recent measurement or the glasses are not available, then the most current prescription in a trial frame can be used.

### **Manifest refraction**

A non-cycloplegic measurement of the refractive error at distance will be performed on the study eye using a phoropter or a trial frame. If the child is wearing a contact lens, this refraction should be done *over* the contact lens. If the child is wearing spectacles, this refraction should be done *without* them.

### **Reading Test**

We will use the ReadAlyzer™ to assess reading speed and comprehension (<http://www.compevo.se/ReadAlyzerInfo.pdf>). The ReadAlyzer system includes specialized goggles that are worn over the child's usual optical near correction. The near interpupillary distance is adjusted for the child's size. To ensure that the goggles are appropriately adjusted to the child, the child will read a short (100-word) passage written at the 1st grade level. If the child is unable to read and comprehend this short passage, the clinic staff will readjust the goggles to ensure proper fit. After proper fit has been ensured, the child will read a standard, grade-appropriate, 800-word passage and then answer a series of 20 comprehension questions. The system comes with software that provides automatic analysis of the number of fixations, the number of regressions, the mean fixation duration, the reading speed (words per minute), grade level equivalent and comprehension. There is no need for head fixation or calibration.

We have chosen to use the ReadAlyzer System in contrast to other standard reading systems such as the Gray Oral Reading Test (GORT) because it is relatively automated which should maximize inter-rater reliability, because it provides information on fixations and saccades

associated with reading and because it assesses silent reading which is salient to children's academic reading during the later years of elementary school.

### **Ocular Alignment and Randot Stereo testing**

Ideally, testing of stereopsis should occur prior to occlusion of one eye for vision testing, motility evaluation, etc.

The Randot Preschool Stereoacuity Test measures random dot stereoacuity from 800 to 40 arc seconds. The test consists of three booklets. Each booklet has two sets of four random dot shapes on one page. One of these images is blank; the other three are pictures that can be seen only when viewed through polarizing lenses. On the opposite of the booklet are non-stereo images of the same shapes. There are six levels of stereoacuity in the test, with two levels in each book. Each level has four rectangles that contain three shapes and one blank.

Ocular alignment will be assessed with the child fixating on an accommodative target in the distance and at near using the simultaneous prism and cover test. The test will be performed by simultaneously covering the fixating eye and placing a prism in front of the deviating eye. Increasing prism powers are placed over the deviating eye until it no longer shifts. The power of the prism used when the deviating eye no longer shifts is the measure of the deviation. If the child cannot fixate on a target due to poor vision, increasing prism powers will be placed over the deviating eye until the pupillary light reflex is symmetrical with the pupillary reflex in the fixing eye (Krimsky test). If the child will not tolerate a prism placed over the deviating eye, a point source of light will be shown on both eyes. The angle of strabismus will then be estimated based on the degree that the pupillary light reflex is decentered relative to the fixing eye (Hirschberg light reflex test).

### **Biomicroscopy**

An examination of the anterior segment will be performed using the slit lamp. In particular, the condition of the cornea, anterior chamber and, after dilation, the status of the media and IOL (if present) will be assessed.

### **Tonometry**

Tonometry will be performed in both eyes at the 10Y study visit while the child is calm and quiet using Goldmann applanation tonometry preferably, but using Icare rebound tonometry (Icare Finland Oy, Helsinki, Finland), or Tonopen (Tono-PenXL, Medtronic Solan, Jacksonville, FL), if necessary. Topical anesthesia is required for performing Goldmann and Tonopen tonometry, but is not needed for rebound tonometry. Rebound tonometry IOP readings on average measure 2 mm higher than Goldmann applanation tonometry (Lambert, 2013). In contrast, a Tonopen tends to underestimate high IOPs (Kooner et al., 1992). An alternative strategy would be to only assess IOP using Goldmann tonometry. However, some 10 year olds will not tolerate Goldmann tonometry, but will tolerate rebound tonometry or a Tonopen. Flemmons and coworkers reported that 3 of 17 children with glaucoma (mean age, 10 years) would not tolerate Goldmann applanation tonometry, but would tolerate IOP assessment using ICare or a Tonopen.

When Goldmann applanation tonometry is used, a drop of topical anesthetic mixed with fluorescein should be placed on the cornea. At least 2 measurements should be obtained that

are within 3 mm Hg of each other. If the readings are more than 3 mm Hg apart, then a third reading should be obtained. The average of the 3 IOP readings should be used as the study IOP. We anticipate that about 10% of the patients in our study will not tolerate Goldmann applanation and will require the IOP be measured with ICare or a Tonpen. If the IOPs obtained with ICare or a Tonopen are normal, no further testing will be performed. However, if the IOP is elevated (>21 mmHg) with ICare and/or Tonopen another attempt will be made immediately to measure the IOP using Goldmann applanation. If the child will still not tolerate Goldmann applanation, another attempt will be made 1-2 hours later after the child has had a lunch or snack and has rested. If the child will still not tolerate Goldmann applanation, arrangements will be made for the child return within 30 days to have the elevated IOP verified using Goldmann applanation. We anticipate that this scenario will occur in fewer than 5 patients.

When using rebound tonometry, the child should be sitting in a chair with the instrument positioned vertically. Icare rebound tonometry measurements should not be taken on a given eye until a long beep is heard, and the instrument panel shows a reliable IOP reading (with no error bar or the error bar on the bottom of the screen). If the error bar is in the middle of the screen, and the IOP reading is below 21 mm Hg, then this is also acceptable as a reading. At least two IOP measurements with reliable readings should be obtained within 3 mm Hg of one another, or a third reading should be taken and recorded. If the error bar is in the middle (with IOP above 20 mm Hg) or at the top of the screen, indicating a less reliable reading, the measurement should be repeated until a reliable reading has been obtained.

When using a Tonopen, the IOP reading should be taken with a 5% confidence interval noted on the instrument. At least 2 readings should be obtained within 3 mm Hg of each other. If the average IOP is > 21 mm Hg with ICare rebound tonometry or a Tonopen, a confirmatory IOP should be measured using Goldmann applanation tonometry.

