### Phase 3 Definition and Diagnosis of Glaucoma:

In Phases 1 and 2, an eye was defined as having glaucoma if the following criteria were present: IOP >21 mmHg with one or more of the following anatomical changes: 1) corneal enlargement; 2) asymmetrical progressive myopic shift coupled with enlargement of the corneal diameter and/or axial length; 3) increased optic nerve cupping defined as an increase of  $\geq 0.2$  in the cup-to-disc ratio, or 4) the use of a surgical procedure for IOP control. An eye was defined as glaucoma suspect if any of the following criteria were present: 1) two consecutive IOP measurements >21 mmHg on different dates after topical corticosteroids had been discontinued without any of the anatomical changes listed above; or 2) glaucoma medications were used to control IOP without any of the anatomical changes listed above.

In Phase 3, an eye will be defined as having glaucoma if the following criteria are present: 1) IOP > 21mmHg; and 2) a progressive increase in cup-disc ratio, cup-disc asymmetry of  $\geq 0.2$ , or focal rim thinning. An eye will be defined as glaucoma suspect if any of the following criteria are present: 1) IOP > 21mmHg; or 2) glaucoma medications are being used to control IOP; or 3) an optic disc suspicious for glaucoma (e.g. increased cup-disc ratio). The criteria which will be used to diagnose glaucoma in Phase 3 will be the same as the criteria used in Phases 1 and 2 of the IATS, with the exception of ocular enlargement criteria. Unlike infants, children aged 5-10 years do not usually exhibit signs of ocular enlargement with elevated IOP. The criteria which will be used to diagnose glaucoma suspect in Phase 3 will also be the same as the criteria used in Phases 1 and 2 of the IATS with the exception that two consecutive IOP measurements >21 mmHg at two different visits will not be included in the definition since children in Phase 3 will only be examined once. In addition, since optic disc photographs will be taken at the 10Y exam, we have added a suspicious optic disc as another criterion for Phase 3. Since some children may be diagnosed as having glaucoma or glaucoma suspect between the five and 10 year evaluations, a review of medical records will be performed for all patients to determine who are classified as glaucoma or glaucoma suspect for Phase 3. This will assist in establishing diagnostic criteria and the age of onset for study purposes.

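### A normal Tonopen reading is accepted as final although the protocol says the device under-reads high pressures, so an occasional primary-endpoint case can be missed

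*Combined protocol and SAP*

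**What the plan says.** All references are to the combined protocol and SAP.

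- **Devices (Chapter 3, Tonometry).** Goldmann applanation is preferred, with ICare rebound tonometry or a Tonopen as alternatives. No order between these two is set. On numbers: "We anticipate that about 10% of the patients in our study will not tolerate Goldmann applanation".
- **Stated device errors (same section).** "Rebound tonometry IOP readings on average measure 2 mm higher than Goldmann applanation tonometry", whereas "a Tonopen tends to underestimate high IOPs". The size of the Tonopen error is not given, nor the pressure at which it begins.
- **Elevated reading (same section).** "if the IOP is elevated (>21 mmHg) with ICare and/or Tonopen another attempt will be made immediately to measure the IOP using Goldmann applanation". Failing that, there is a further attempt 1-2 hours later and then a return visit within 30 days. The instructions for the individual devices repeat the rule: if the ICare or Tonopen average exceeds 21 mm Hg, "a confirmatory IOP should be measured using Goldmann applanation tonometry".
- **Normal reading (same section).** "If the IOPs obtained with ICare or a Tonopen are normal, no further testing will be performed".
- **Endpoint (Chapter 1, Phase 3 Definition and Diagnosis of Glaucoma).** "An eye will be defined as glaucoma suspect if any of the following criteria are present: 1) IOP > 21mmHg". IOP medication or a suspicious disc also qualifies. Phase 3 glaucoma requires IOP above 21 mmHg together with a disc finding.
- **Analysis (Chapter 5, Statistical Analysis).** The primary comparison is the percentage with glaucoma or glaucoma suspect at 10 years. Glaucoma alone is secondary.

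**The concern.** One verification rule covers two devices that, by the protocol's own account, err in opposite directions. For ICare the rule fits: its stated error is a false high, and Goldmann checks that. For the Tonopen it does not fit: its stated error is a false normal, and a normal result ends IOP testing.

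This reaches the endpoints in two ways. An eye whose only qualifying feature is raised pressure drops out of the primary composite. An eye with disc change and a falsely normal pressure falls from glaucoma to suspect, which affects the secondary endpoint and the three-category model.

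Little in the plan would repair this later. Phase 3 has a single study examination. The missing-data methods address children whose status was not verified at 10 years, and a child with an accepted normal reading is not one of them.

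**Working it through.** **1. The plan's own expectation.** The plan expects about 10% not to tolerate Goldmann, and fewer than 5 patients to have an elevated ICare or Tonopen reading that Goldmann still cannot verify. It gives no derivation, so only a consistency check is possible. 0.10 × 114 = 11.4 children. Multiplying by the 5-year glaucoma/suspect rates (IOL 28%, CL 35%) gives 3.2 to 4.0, which agrees with fewer than 5. The 5-year rate is only a stand-in for the share with raised pressure at the visit.

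**2. Chance that a truly raised pressure reads as normal.** Let T be the true (Goldmann) pressure, b the device bias and SD the error of the recorded value. Then P(reading ≤ 21) = Φ((21 − T − b)/SD). The ICare b = +2 is from the protocol. The Tonopen values of b, and SD = 2 to 3 mm Hg, are assumptions.

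| Device | T = 22 | T = 24 | T = 26 |
|---|---|---|---|
| ICare, b = +2 | 7-16% | 1-5% | 0-1% |
| Tonopen, b = 0 (noise only) | 31-37% | 7-16% | 1-5% |
| Tonopen, b = −1 | 50% | 16-25% | 2-9% |
| Tonopen, b = −2 | 63-69% | 31-37% | 7-16% |
| Tonopen, b = −4 | 84-93% | 63-69% | 31-37% |

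Example: T = 24, b = −2, SD = 2 gives Φ(−0.5) = 31%.

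**3. Children at risk of being missed.** Diagnoses made by age 5 are retained: 0.35 × 57 ≈ 20 and 0.28 × 57 ≈ 16, together 36. That leaves 114 − 36 = 78 who could be missed for the primary endpoint, of whom 0.10 × 78 = 7.8 would not have a Goldmann reading. Further assumptions: 25-75% of these are measured by Tonopen, and 10-30% of those have true IOP above 21.

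- True elevations resting on a Tonopen: 7.8 × 0.25 × 0.10 = 0.2 to 7.8 × 0.75 × 0.30 = 1.8.
- Of these, read as normal (31-69%, from b = −2 and T = 22 to 24): 0.2 × 0.31 = 0.06 to 1.8 × 0.69 = 1.2.
- With no other route to the endpoint (one half, assumed): about 0.03 to 0.6.

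**4. Harsher inputs.** The Tonometry section cites 3 of 17 children with glaucoma (17.6%) as not tolerating Goldmann. Applied to all 78, this gives 13.8 children, and 13.8 × 0.75 × 0.30 × 0.69 = 2.1 read as normal. With b = −4 as well (93%), the figure is 2.9. Halving for other routes gives 1.1 and 1.4.

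**5. Effect on the comparison.** One case is 1/57 = 1.75 percentage points of an arm. The documents' text gives no Phase 3 power figure, so as an illustration take assumed 10-year rates of 56% (CL) and 28% (IOL), with 57 per arm and two-sided Fisher's exact test at 0.05. Expected cases are 57 × (0.56 + 0.28) = 47.9.

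| Tonopen share of the 10% | Cases missed among them | Cases lost | Power |
|---|---|---|---|
| none | none | 0 | 81.5% |
| half | 25% | 47.9 × 0.0125 = 0.6 | 80.6% |
| all | 50% | 47.9 × 0.05 = 2.4 | 77.7% |
| all | 100% | 47.9 × 0.10 = 4.8 | 73.8% |

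These rows apply the loss to every case, including the 36 retained diagnoses that cannot be lost, so they overstate it. The last row is a bound, not a forecast.

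**The case against.** The strongest reply is that the gap hardly matters and is partly deliberate.

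- **Deliberate trade-off.** Chapter 1 worries that pressure-only definitions over-diagnose glaucoma and that thick aphakic corneas add error, so confirming high readings serves a stated aim. The Tonometry section also considers a Goldmann-only strategy and declines it. This explains why highs are confirmed. It does not explain why a normal from a device said to read low is left alone.
- **Where the error begins.** If under-reading matters only well above 21, the reading would still exceed 21 and go to Goldmann. This stands: misclassification at the cut-off is an inference.
- **Other routes to the endpoint.** Medication, stereo disc photographs graded by three experts, record review for all patients and retained diagnoses will catch some of these eyes. This stands, and is why the loss is small.
- **Few Tonopen readings.** ICare is named first, needs no anesthetic drop and was widely used in the earlier phases. A low Tonopen share is plausible, but the protocol sets no order.

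Three stronger readings are tempting and are not supported. First, a reader might infer that missed cases differ by arm, for example because contact-lens wearers tolerate Goldmann better. Nothing in the documents links the two, and 3 + 16 = 19 of the 57 CL children are already recorded as having secondary IOLs. Second, the ICare instructions accept a mid-screen error bar when "the IOP reading is below 21 mm Hg, then this is also acceptable as a reading" but require a repeat above 20. This looks like a laxer standard for normals, but the bar concerns reliability, ICare is said to read high, and no effect on classification is shown. Third, all 11.4 children at the same assumed shares give 0.3 to 2.6 true elevations measured by Tonopen (11.4 × 0.25 × 0.10 to 11.4 × 0.75 × 0.30). Those are not missed cases: some would still read above 21, and some qualify by another route.

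**Conclusion.** The point holds, limited to normal Tonopen readings in children who do not tolerate Goldmann. The protocol attributes a specific error to the device and leaves that error unchecked, in a measurement that alone can decide the primary endpoint. The likely loss is 0 to 1 primary-endpoint case, about 2 at most once other routes are allowed for. It is non-differential as far as the documents show: mild under-ascertainment, not a demonstrated bias between arms. A few eyes might also move from glaucoma to suspect in the secondary analysis.

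The size rests on the plan's 10% expectation and on assumed values for the Tonopen share, the prevalence of raised pressure, the Tonopen bias and SD, and the share of eyes caught otherwise. The mechanism itself needs only the protocol's text. This is a minor point, worth correcting because correction is cheap and new diagnoses between 5 and 10 years are what the Phase 3 hypothesis concerns.

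**What to change.** Reconcile the verification rule in the Tonometry section with the device errors stated there, for the endpoint measurement:

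1. Where ICare is available, make it the first fallback after Goldmann, and use the Tonopen only if ICare also fails.
2. Repeat a Tonopen-only normal reading with ICare or Goldmann at the same visit.
3. Record on the eCRF which device gave the study IOP. The forms are in an appendix not among the documents, so this field may already exist.
4. If only a normal Tonopen reading can be obtained, keep the child in the primary analysis with the status as recorded. Add a sensitivity analysis that treats the IOP criterion as uncertain: count these eyes first as not meeting it and then as meeting it. This extends the approach Chapter 5 already plans for children not examined at 10 years. Do the same for the secondary endpoint where a disc finding is present.

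Do not code such readings as unverified. The available-case analysis in Chapter 5 excludes children whose status is not verified, so that coding could remove more children than the cases it recovers.

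The cost is protocol wording, possibly one eCRF field, and a few minutes of repeat readings in some of about 11 children. Because ICare reads about 2 mm high, a few more Goldmann confirmations or return visits may follow. The documents do not say that every site has ICare, hence the condition in step 1.

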### **Pupils**

Pupils will be assessed for size (diameter in millimeters), shape (round or not), and position (central or eccentric).

### **Cycloplegic Refraction**

A cycloplegic refraction of both eyes will be performed without external correction (ie, *not over contact lens or spectacles*) and using a phoropter or trial frame. Enough dilation should be achieved to accommodate later fundus imaging.

### **E-ETDRS Acuity Assessment after Cycloplegic Refraction**

#### **Monocular Visual Acuity Testing – Recognition Acuity**

Visual acuity measures will be standardized at each clinical site by using the Electronic Visual Acuity Tester (EVAT). The EVAT runs a visual acuity testing program called E-ETDRS. This program was developed to provide a visual acuity letter score that is comparable to the ETDRS chart testing score. Visual Function Examiners (VFE) will have been certified to perform vision testing according to the protocol. Visual acuity will first be tested binocularly and then monocularly for each eye.

### **Electronic Visual Acuity Tester (EVAT)**

The EVAT is an automated system that displays the acuity stimuli on a monitor. It uses a programmed Palm handheld device (or tablet PC) that communicates with a personal computer running a Linux (or Windows) operating system. This system was developed by JAEB for the ATS projects. Ten IATS sites use this system in their clinics; the other 2 sites have the E-ETDRS test available on the M&S acuity tester. VFE certification will occur via an online test at PEDIG sites and will be a paper test created by the JAEB Center for non-PEDIG sites.

### **Optical Correction**

If the child was wearing a CL, the lens should be replaced on the study eye and any residual correction placed in a trial frame. Any correction needed for the fellow eye will also be placed in the trial frame. If the child normally wears spectacles, the vision should not be tested using them as there may be imperfections in the lenses. Instead the cycloplegic refraction should be placed in a trial frame.

### **Monocular Occlusion**

A translucent occluder will be used to minimize the presence of latent nystagmus under monocular conditions. If this type of occluder is not available, an appropriate high plus power (e.g., +10D) lens may be used

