### **Inclusion Enrollment Report**

We enrolled 114 children in IATS between 12/04 and 1/09. All study patients were between the ages of 28 and 210 days at the time of enrollment. The patients all had a unilateral congenital cataract and the fellow eyes were normal. Only infants were enrolled in the study because our goal was to compare two optical treatments for infants following infantile cataract surgery. The ethnicity and gender of the patients enrolled in IATS is shown in Table 7. The clinical trial is being conducted at 12 clinical sites. The DCC and the chairman's office are located at Emory University.

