### **Range of Testable Acuity**

If the child is unable to see the largest (20/800) stimulus at the 3M testing distance, the testing will be conducted at 1 meter. The same procedure will be followed at 1 meter as was used at 3 meters. If the child is unable to detect the 20/800 stimulus at 1 meter (ie, VA < 20/2400), then the E-ETDRS testing will be stopped for this eye and the test for Hand Motion will be performed.

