### **Assessment of Hand Motion Vision**

The examiner's hand is extended to about two feet in front of the eye being tested; the fellow eye is occluded. With a light shining from behind the patient onto the examiner's hand, the hand is moved either up-and-down or side-to-side in front of the eye at a steady speed of about one cycle/second. The patient is asked to identify the direction of motion of five separate trials. Four out of five correct responses indicate the presence of Hand Motion vision. If fewer than four responses are correct, check for Light Perception vision.

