### **Assessment of Light Perception**

Children who are unable to perform E-ETDRS or Hand Motion testing in the treated eye will have that eye assessed for the presence of light perception (LP). LP will be tested with an indirect ophthalmoscope. Testing for LP will take place in a darkened room. Because the LP testing needs to be done monocularly, it is necessary to block the eye not being tested from all possible light to preserve accuracy. Standard eye patches alone do not achieve complete occlusion, and for this reason the tester, parent, or helper will place the palm of his or her hand gently but firmly over the patched eye thereby blocking out all light. The bright light from the indirect ophthalmoscope will then be directed at the uncovered eye 3 or 4 times from the front and sides at 18 – 24 inches from the face to avoid exposing the child to the heat of the light. The tester will ask the child to respond when the light is seen or to watch for consistent changes in

behavior occurring only when the light is being presented, such as eye movement towards or away from the light or head turn towards or away. If the examiner is convinced that the child does not perceive light, the vision will be recorded as No Light Perception.

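### The fallback plus-lens occluder does not exclude a normal fellow eye at 1 metre, so where it is used a study eye worse than 20/2400 can be given the fellow eye's letter score

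*Combined protocol and SAP*

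**What the plan says.** All the testing rules are in Chapter 3.

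- **Monocular Occlusion** sets the first choice: "A translucent occluder will be used to minimize the presence of latent nystagmus under monocular conditions". If that device is not available, "an appropriate high plus power (e.g., +10D) lens may be used". No test distance is attached to either option.
- **Range of Testable Acuity** sends an eye that cannot see the largest stimulus (20/800) at 3 m to testing at 1 m, and adds: "The same procedure will be followed at 1 meter as was used at 3 meters". Failure at 1 m, which the protocol equates with acuity below 20/2400, ends letter testing and leads to the hand-motion test.
- **Assessment of Hand Motion Vision** places the hand at about two feet with the fellow eye occluded, but names no device. Four correct of five is a pass. Otherwise: "If fewer than four responses are correct, check for Light Perception vision".
- **Assessment of Light Perception** is the only step that specifies full light exclusion. It notes that "Standard eye patches alone do not achieve complete occlusion" and adds a palm over the patch.

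Three other statements bear on the fellow eye. Under Inclusion Enrollment Report: "The patients all had a unilateral congenital cataract and the fellow eyes were normal". Under Optical Correction: "Any correction needed for the fellow eye will also be placed in the trial frame". Under Cycloplegic Refraction, which precedes the acuity test: "Enough dilation should be achieved to accommodate later fundus imaging".

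**The concern.** The tests form a ladder: letters at 3 m, letters at 1 m, hand motion, light perception. A study eye reaches the fully occluded step only by failing the steps before it. If the cover used at 1 m lets the good eye see the target, the child passes with the wrong eye and the ladder stops there. The protocol describes no check that the covered eye cannot see the target.

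At stake is whether the lowest acuity values are correct. The Visual Acuity paragraph of Chapter 5 plans a linear regression of acuity on baseline factors and says the transformation must deal with the floor values of eyes that see very poorly. Those values are the ones that could come from the fellow eye. The protocol text does not ask for the occlusion method to be recorded, so affected results could not be picked out later unless the forms, which are not among the documents, capture it.

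**Working it through.** **The plan's own figure.** Moving the 20/800 stimulus from 3 m to 1 m multiplies the Snellen denominator by 3/1: 800 × 3 = 2400. This reproduces the protocol's 20/2400.

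**Inputs from the protocol.** The lens is +10 D (its example). Distances are 3 m, 1 m and about two feet (0.61 m). The fellow eye is normal and wears any correction it needs, so the lens acts as roughly +10 D of net fog. The eye is cyclopleged.

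**Inputs assumed.** The documents give no pupil diameter; I take 6–8 mm, with 3 mm as a check. A letter is taken as legible when its height is at least *k* blur discs, with *k* from 1 to 2. The hand is taken as 8 cm wide.

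**Formulas.**

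- Net defocus (D) = 10 − 1/distance (m).
- Blur disc (arcmin) = pupil (m) × defocus (D) × 3437.7.
- Letter height = 5 × minimum angle of resolution: 5 × 40 = 200 arcmin for 20/800 at 3 m, and 5 × 120 = 600 arcmin for the same letter at 1 m.
- Hand = arctan(0.08/0.61) ≈ 7.5 degrees.

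**Results for a 6–8 mm pupil.**

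| Target | Net defocus | Blur disc | Target size | Target ÷ blur |
|---|---|---|---|---|
| Largest letter, 3 m | 9.67 D | 199–266 arcmin | 200 arcmin | 1.00–0.75 |
| Same letter, 1 m | 9.00 D | 186–248 arcmin | 600 arcmin | 3.23–2.42 |
| Hand, 0.61 m | 8.36 D | 2.9–3.8 degrees | about 7.5 degrees | about 2.6–2.0 |

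For example, at 1 m with a 6 mm pupil: 0.006 × 9.00 × 3437.7 = 186 arcmin, and 600/186 = 3.23.

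**Reading the table.** At 3 m the fogged eye is at or beyond the limit of legibility by the one-disc criterion. At 1 m the letter triples in angular size while the blur shrinks slightly, so the letter is legible even when two discs are required. A smaller pupil makes the 1 m problem worse: at 3 mm the letter is 600/93 ≈ 6.5 discs tall. The conclusion would fail only if a letter had to exceed about 2.4 discs (8 mm pupil) to 3.2 discs (6 mm pupil).

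**Power needed to fog the 1 m letter.** Setting the blur equal to 600/*k* gives power = 600/(*k* × pupil × 3437.7) + 1. For 6–8 mm pupils this is about 12–16 D when *k* = 2 and 23–30 D when *k* = 1. The protocol's example power is below both ranges.

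**The case against.** The strongest reply is that the lens is a fallback. The protocol names the translucent occluder first, allows the lens only in its absence, requires it to be appropriate, and gives +10 D as an example. Nothing shows that any site lacks the first-choice device, and the Manual of Procedures and the examiner certification material, neither of which is in the documents, may settle the matter. All of this stands, and it limits how often the problem can arise. It does not remove the problem, because the text as written permits the example lens at 1 m.

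The hand-motion part is also open to dispute. The occlusion rule sits among the letter-testing instructions, letter testing has stopped by then, and the light-perception section speaks of an eye already patched. A patch may be what was meant. The point reaches hand motion only if the requirement to occlude is read back through Monocular Occlusion, the only earlier definition.

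The reply is strong on consequences too. The Wilcoxon test uses ranks, and affected eyes stay near the bottom. The alternative logistic model asks whether acuity is within normal limits, and moving an eye from no light perception to a 1 m letter score cannot change that answer. The transformation planned for the linear regression may itself damp the lowest values.

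A reader might go further and infer that blind-eye counts by arm are distorted. No such count is among the planned analyses. A reader might also infer that the translucent occluder fails. The calculation concerns the lens only, and nothing in the documents faults the translucent device.

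**Conclusion.** The point holds in limited form. Where the fallback lens is used at about the example power, the procedure does not exclude a normal fellow eye at 1 m. A study eye worse than 20/2400 can then be recorded with a 1 m letter score and miss the valid test for light perception. On the conditional reading above, the same applies to hand motion. This rests on the assumed pupil range and legibility criterion, and holds throughout both.

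The number of eyes cannot be derived. A reader might assume that 5–10% of eyes fall below 20/800 and infer about 3–6 per arm (0.05 × 57 = 2.9; 0.10 × 57 = 5.7). The documents do not support that. They give no such share, eyes between 20/800 and 20/2400 earn a 1 m letter result in their own right, and use of the lens is unknown. The true number is probably very small and could be zero. Nor should the lens be taken as proven safe at 3 m, where a 6 mm pupil gives a ratio of only 1.00.

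The main exposure is the bottom-of-scale values in the exploratory acuity regression. The Wilcoxon comparison is little affected and the glaucoma endpoint is untouched. This is a low-priority clarification.

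**What to change.** In Monocular Occlusion, Range of Testable Acuity and Assessment of Hand Motion Vision, state that the plus-lens fallback is not used for letters at 1 m or for hand motion. If no translucent occluder is available at those steps, cover the fellow eye with the patch plus palm already described for light perception. Keep the translucent occluder as first choice throughout. Record occlusion type and test distance on the eCRF.

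The cost is about one sentence and two eCRF fields, with no new equipment. The downside is that opaque cover may bring out latent nystagmus, the problem the translucent occluder is meant to limit. That would arise only in the few eyes that cannot see 20/800 at 3 m, and only when the preferred occluder is missing.
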